### **Power Analysis**

Power is calculated for differences in baseline to week 12 change scores. Testing for treatment x time interactions and # at .05, we have 80% power to detect moderate to large effects.

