**To Complete Study**

**Feasibility of Meeting Recruitment Goals**

Power is calculated for differences in baseline to week 12 change scores. Testing for treatment x time interactions and # at .05, we have 80% power to detect moderate to large effects.

Based on data from our previous clinical trial of IGF-1 in patients with Phelan McDermid Syndrome, a 12 week study was feasible in 9 patients.

We feel that 20 patients would provide adequate data to establish the utility of growth hormone in this population. The Seaver Autism Center has access to this population of children with Phelan McDermid Syndrome which should help facilitate recruitment.

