### **Drug Administration**

Growth hormone will be administered subcutaneously once daily using a 12-week single group design. No placebo will be used. The 12-week duration was selected because of our previous trial with IGF-1 showing effects in standardized behavior scales in that duration, hence establishing proof of concept.

The dose of daily growth hormone varies with the indication for therapy. Approved doses of growth hormone range from 0.16-0.25mg/kg/week for growth hormone deficient patients (Grimberg et al.; 2016) and up to 0.47 mg/kg/week for patients born small for gestational age.

In our proposed trial, we expect a majority of our patients to be growth hormone sufficient and therefore similar to the population of children with idiopathic short stature treated with growth hormone. We will recommend a dose of 0.15mg/kg/week divided daily for 2 weeks as a starting dose to ensure safety and tolerance. The dose will then be increased to 0.3mg/kg/week for 10 weeks, an average growth hormone dose in children with idiopathic short stature.

The growth hormone dose will be titrated based on IGF-1 levels monitored serially up to a maximum dose of 0.45mg/kg/week. (<http://www.ferringusa.com/wp-content/uploads/2018/07/ZOMACTON-PI-7-18.pdf> )

Drug dose is calculated on a mg/kg/week basis. Using Center for Disease Control average Weight-for-age statistics in typically developing children ages 2 to 12 years ([www.cdc.gov/growthcharts/cdc\\_charts.htm](http://www.cdc.gov/growthcharts/cdc_charts.htm)), the overall average weight across a representative sample of males and females in this age range is 24.65kg.

Average growth hormone dose for weeks 1-2: 0.15mg \* 24.65kg per week = 3.7 mg per week

Average growth hormone dose for weeks 3-10: 0.3mg \* 24.65kg per week = 7.4 mg per week

With a recruitment target of 20 patients, we anticipate the need for a total of 1628 mg of growth hormone with each person requiring about 81 mg of growth hormone in 12 weeks. We anticipate the need for 17 vials of growth hormone (10 mg per vial).

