### **Power Analysis/Data Analysis Plan (Including Any Statistical Procedures)**

The model for this design is baseline to week 12 change scores. To examine whether electrophysiological markers track changes in clinical profiles, we will fit an additional GLMM with VEP values included as a time-varying rather than baseline covariate. If treatment effects become less significant it will suggest that GH is acting on clinical outcomes through the biomarker. Finally, we will directly correlate week-12 change scores for VEP and clinical measures. All tests will use a two-sided # of .05.

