### **Selection Procedures to Minimize Toxicity**

Growth hormone will be administered subcutaneously once daily using a 12-week single group design. No placebo will be used. The 12-week duration was selected because of our previous trial with IGF-1 showing effects in standardized behavior scales in that duration, hence establishing proof of concept.

The dose of daily growth hormone varies with the indication for therapy. Approved doses of growth hormone range from 0.16-0.25mg/kg/week for growth hormone deficient patients (Grimberg et al.; 2016) and up to 0.47 mg/kg/week for patients born small for gestational age.

In our proposed trial, we expect a majority of our patients to be growth hormone sufficient and therefore similar to the population of children with idiopathic short stature treated with growth hormone. We will recommend a dose of 0.15mg/kg/week divided daily for 2 weeks as a starting dose to ensure safety and tolerance. The dose will then be increased to 0.3mg/kg/week for 10 weeks, an average growth hormone dose in children with idiopathic short stature. The growth hormone dose will be titrated based on IGF-1 levels monitored serially up to a maximum dose of 0.45mg/kg/week. (<http://www.ferringusa.com/wp-content/uploads/2018/07/ZOMACTON-PI-7-18.pdf> )

Drug dose is calculated on a mg/kg/week basis. Using Center for Disease Control average Weight-for-age statistics in typically developing children ages 2 to 15 years ([www.cdc.gov/growthcharts/cdc\\_charts.htm](http://www.cdc.gov/growthcharts/cdc_charts.htm)), the overall average weight across a representative sample of males and females in this age range is 30kg.

Average growth hormone dose for weeks 1-2:  $0.15\text{mg} * 30\text{kg per week} = 4.5\text{mg per week} = 0.6\text{mg per day}$

Average growth hormone dose for weeks 3-10:  $0.3\text{mg} * 30\text{kg per week} = 9\text{mg per week} = 1.3\text{ mg per day}$

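### The 80% power is claimed for a treatment-by-time interaction that a single-group trial cannot estimate, and a weaker effect after adding VEP is read as GH acting through the biomarker

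*Combined protocol and SAP*

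**What the plan says.** The design has one arm. Section 12 (Drug Administration) describes treatment "using a 12-week single group design. No placebo will be used", and Section 22 (Selection Procedures to Minimize Toxicity) repeats it: "Growth hormone will be administered subcutaneously once daily using a 12-week single group design". The grant title in Section 23 calls the trial open label.

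The power statement is two sentences in Section 21 (Power Analysis): "Power is calculated for differences in baseline to week 12 change scores", then "Testing for treatment x time interactions and # at .05, we have 80% power to detect moderate to large effects". Both recur in Section 7 (Feasibility of Meeting Recruitment Goals), which adds that in the earlier IGF-1 trial "a 12 week study was feasible in 9 patients". Neither place gives a numerical effect size, an SD of change, a dropout rate or the outcome to which the power applies.

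The data analysis plan in Section 21 begins "The model for this design is baseline to week 12 change scores". It adds a GLMM with VEP as a time-varying covariate and gives a rule for reading it: "If treatment effects become less significant it will suggest that GH is acting on clinical outcomes through the biomarker". It closes with "Finally, we will directly correlate week-12 change scores for VEP and clinical measures", all tests being two-sided at .05. Section 3 (Objectives, item 2) names the ABC Social Withdrawal subscale as the primary outcome measure.

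**The concern.** A treatment-by-time interaction asks whether change over time differs between treatment groups. With one group there is no such difference to estimate, so the 80% is attached to a test the trial cannot run. The adjacent sentence names a quantity that can be tested, the change within each child, but the text does not say what size of change the 80% refers to. The reader must guess the test, and the answer depends strongly on the guess.

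The VEP rule inherits the problem. In one treated group, the treatment effect in the model is simply the time effect. It mixes any action of GH with maturation, regression to the mean and expectancy in an unblinded, caregiver-rated scale. If adding VEP weakens that effect, nothing in the data says which of these VEP is tracking, or whether the standard error has merely grown. Followed as written, the rule could put a mechanistic conclusion about GH into the report that uncontrolled data cannot support.

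**Working it through.** **Inputs from the document:** 20 children, one group, two-sided .05, 80% power, baseline to week 12 change. **Assumed:** 0.5 and 0.8 as moderate and large standardized effects, the numbers of completers below 20, the two-group split, and all simulation values. No SD of change is given, so effects are in SDs of the change score.

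**1. Can the interaction be estimated?** Take 20 children at two visits, with columns for intercept, treatment, time and treatment × time. With treatment equal to 1 throughout, the treatment column equals the intercept and the interaction column equals time, so the rank is 2 of 4. Coding treatment 0 at baseline and 1 at week 12 also gives rank 2. The plan's 80% therefore cannot be reproduced for the test it names.

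**2. Paired change.** Power = P(|T| > t₀.₉₇₅,ₙ₋₁), where T is noncentral t with n − 1 df and noncentrality d√n. Check by normal approximation at n = 20: (1.960 + 0.842)/√20 = 0.63. The exact value is 0.66.

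| Children with week 12 data | Change (SD) for 80% power | Power at 0.5 | Power at 0.8 |
|---|---|---|---|
| 20 | 0.66 | 56% | 92% |
| 17 | 0.72 | 49% | 87% |
| 15 | 0.78 | 44% | 82% |

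The smallest n for 80% power is 34 at 0.5 SD and 15 at 0.8 SD.

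**3. The interaction taken literally.** This needs two groups; 10 and 10 is assumed. The normal approximation is 2.802 × √(2/10) = 1.25, and the t-test gives d = 1.32. Power is 18.5% at 0.5 and 39.5% at 0.8; reaching 80% would need 64 or 26 per group. The stated 80% fits only the paired reading.

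**4. The VEP rule.** With two visits, a within-child model with time-varying VEP reduces to ΔY = b₀ + b₁ΔVEP + error, and the adjusted time effect is b₀. The variance of b₀ is proportional to 1/n + (mean ΔVEP)²/SS(ΔVEP). If VEP shifts by 0.66 SD and is unrelated to outcome, the standard error grows by about √(1 + 20 × 0.66²/19) = 1.21, with no mediation at all.

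I simulated 100,000 trials per cell: n = 20, outcome change N(0.66, 1), VEP change N(shift, 1), correlation r between the two changes. Each cell shows the share of trials in which the p-value for time rises, then the share of initially significant trials that lose significance.

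| r | VEP shift 0 | 0.3 | 0.5 | 0.66 |
|---|---|---|---|---|
| 0 | 73% / 5% | 75% / 10% | 79% / 17% | 81% / 25% |
| 0.3 | 53% / 4% | 86% / 19% | 96% / 37% | 98% / 52% |
| 0.5 | 31% / 3% | 78% / 23% | 95% / 48% | 98% / 67% |
| 0.7 | 13% / 1% | 63% / 21% | 91% / 56% | 97% / 80% |

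The top row has no link between VEP and outcome, yet the rule would usually be met if any rise in p counts as less significant. The lower rows have a link but no drug term, so the rates are the same whether GH or maturation causes the changes.

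**5. Precision of the planned correlation.** With 20 children and r = 0, the 95% limits are ±tanh(1.96/√17) = ±0.44.

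**The case against.** **Change scores are named.** The sentence before the interaction sentence, and the analysis plan, both refer to baseline to week 12 change. The detectable 0.66 SD lies between 0.5 and 0.8, so moderate to large is a fair description of a paired test, and the moderate cut-off of 0.5 is mine. This stands as far as it goes: the sample size is not undermined. It does not supply the missing effect size or make the named test possible.

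**The interaction could mean GH against the earlier IGF-1 trial.** Several hypotheses in Section 3 compare the two. That contrast would be estimable, but no pooled or historical-control model is given, and 20 against 9 children would need a difference of about 1.17 SD for 80% power.

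**There are more than two visits.** Section 12 schedules weeks 4, 8 and 12 and a visit 4 weeks after therapy. Coded off, on, on, on, off, treatment is no longer collinear with linear time. But no such coding is specified, the stated model is baseline to week 12, the document does not clearly say that ABC or VEP is repeated after therapy, and on/off coding would not remove expectancy.

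**The VEP rule is hedged and additional, and the simulation rests on assumed values.** True: the p-value rises in anything from 13% to 98% of trials, so no single rate should be quoted as the error rate. The argument is conceptual, and the simulation only illustrates it. A hedged rule still pre-specifies a mechanistic reading.

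**An attached research plan was not available.** It may hold an effect size or SD. Nothing in it could make the interaction estimable in one group.

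**Conclusion.** The concern holds and should be fixed. The stated power belongs to a test that the trial, as designed and modelled, cannot perform. Read as a paired test it is roughly right at the larger end: 80% at 0.66 SD of change with all 20 children, but only 56% at 0.5 SD, and less if children are lost. Those figures assume a t-test on change, and 0.5 as the meaning of moderate.

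The VEP rule is the more consequential half. A less significant time effect is not evidence that GH acts through VEP, because in this design the same result arises from causes unrelated to the drug and from a larger standard error alone. That conclusion follows from the absence of a control and does not depend on the simulation inputs.

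**What to change.** 1. In the Power Analysis (Section 21) and its copy in Section 7, replace the interaction sentence with:

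> With 20 completers, a two-sided .05 paired test of baseline to week 12 change has 80% power for a mean change of 0.66 SD of change (56% for 0.5 SD, 92% for 0.8 SD).

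Name the outcome it applies to (Section 3 points to ABC Social Withdrawal). Show the effect of fewer completers as a labelled assumption, for example 0.72 SD with 17. If the sponsor holds an SD of change from the earlier IGF-1 trial, give the detectable change in scale points as well. If a comparison with the IGF-1 children was in fact meant, write out that model and its own power.

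2. In the data analysis plan, replace the sentence inferring action through the biomarker with:

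> Change over time with and without VEP will be described as exploratory; without a control group it does not show that GH acts through VEP.

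Keep the planned correlation of week 12 change scores and report it with its 95% confidence interval, as an association.

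**Cost:** wording in three places, with no added patients, visits or data. The power statement becomes slightly less favourable and the mechanistic conclusion is given up.

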**Other External Site Name**

**Contact Details**

**Approved**

**Approval Document**

**Funded By Mount Sinai**

**Other IRB**

**6. Subjects - Enrollment**

**Site Name** Icahn School of Medicine at Mount Sinai  
**Subjects To Be Enrolled** 20  
**Total Number of Subjects to be Enrolled Across All Listed Sites Above (Auto Populated)** 20

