**Specify Other Setting of Human Research**

Seaver Autism Center for Research and Treatment at Icahn School of Medicine at Mount Sinai

**Total Number of Subjects Needed** 20

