## **12. Procedures - Narrative**

### **Description of the Study Design**

The proposed pilot will seek to recruit 20 children aged 2 to 12 years old with SHANK3 deletions or mutations and with radiographic evidence of open epiphyses. Phenotype definition will be conducted using a comprehensive assessment battery, including: (1) psychiatric evaluation; (2) clinical genetics evaluation; (3) neurological examination; (4) Vineland Adaptive Behavior Scales. The study will include newly recruited children in addition to those who have been previously recruited for the purposes of genetic studies by the Seaver Autism Center.

Patients recruited will have screening prior to trial and will then follow up at 4 weeks, 8 weeks and 12 weeks of therapy with growth hormone daily injections. A 4 week post therapy follow up will also be arranged.

Inclusion criteria:

Diagnosis: Pathogenic deletions or mutations of the SHANK3 gene confirmed by array CGH and/or direct sequencing.

Age Range: Cases will be between 2 and 12 years old at the time the phenotypic measures were collected.

Exclusion criteria:

Cases will be excluded if any of the following criteria are applicable:

closed epiphyses;

active or suspected neoplasia;

intracranial hypertension;

hepatic insufficiency;

renal insufficiency;

cardiomegaly/valvulopathy;

history of allergy to growth hormone or any component of the formulation (mecasermin);

history of extreme prematurity (<1000 grams) with associated early neo-natal complications, e.g. intra-cerebral hemorrhage, prolonged hypoxia, prolonged hypoglycemia;

patients with comorbid conditions who are deemed too medically compromised to tolerate the risk of experimental treatment with growth hormone.

Patient with visual problems that preclude the use of VEPs

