### **Specific Items That Will Be Monitored for Safety**

Adverse effects from growth hormone administration, subject compliance, drop outs

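### The 80% power claim has no numeric effect size and names an untestable interaction; with 20 children in one group it starts at 0.66 SD of the change and covers 0.5 only under assumptions not stated

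*Combined protocol and SAP*

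**What the plan says.** Section 21, Power Analysis, says that power was computed for baseline-to-week-12 change scores, through a treatment x time interaction at .05, and concludes "we have 80% power to detect moderate to large effects". Section 7, Feasibility of Meeting Recruitment Goals, repeats this and, after a sentence on the nine-patient IGF-1 trial, adds: "We feel that 20 patients would provide adequate data to establish the utility of growth hormone in this population".

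The other inputs are spread through the document:

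- **Sample size.** Section 12, Description of the Study Design: "The proposed pilot will seek to recruit 20 children aged 2 to 12 years old". Section 6 enters 20 against "Subjects To Be Enrolled", and section 7 enters 20 again against a label that begins "Total Number of Subjects Needed".
- **Design.** Section 12, Drug Administration: "using a 12-week single group design. No placebo will be used".
- **Test level.** Section 21, data analysis plan: "All tests will use a two-sided # of .05" (the # is a lost alpha symbol).

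Nowhere is there a numeric effect size, a standard deviation, a baseline-to-week-12 correlation, a drop-out rate or a power formula.

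**The concern.** The power sentence has two faults. First, it names a test that the design cannot run: a treatment x time interaction needs a comparison group, and there is none. Second, it describes the detectable effect only in words. A reader will usually take moderate as about 0.5 SD and large as about 0.8 SD, and will understand that a moderate effect would be found four times in five. For 20 children and a test of mean change, that is not so if the 0.5 is measured in SDs of the change.

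What is at stake is how the main result is read. Section 3 (Objectives) makes ABC-Social Withdrawal the primary outcome. If the test is not significant, someone relying on the stated 80% could take that as evidence against a moderate benefit, which a trial of this size may not be able to give.

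**Working it through.** **Inputs.** From the documents: n = 20, one group (section 12); two-sided alpha .05 and baseline-to-week-12 change scores (section 21); stated power 80% (sections 7 and 21). Assumed, because the documents give no number: moderate = 0.5 and large = 0.8, the usual convention.

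**Reproducing the plan's figure.** This cannot be done directly, since 80% is attached to no effect size. The check is to find the effect at which 80% is reached.

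**Step 1: effect in SDs of the change score.** Let d = mean change / SD of change. The test statistic is noncentral t with n - 1 degrees of freedom and noncentrality d x sqrt(n). Power is the probability that its absolute value exceeds the critical t. For n = 20, the critical value on 19 degrees of freedom is 2.093, and at d = 0.5 the noncentrality is 0.5 x sqrt(20) = 2.236.

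| Children with a week-12 score | Power at 0.5 | Power at 0.6 | Power at 0.8 | d giving 80% power |
|---|---|---|---|---|
| 20 | 56% | 72% | 92% | 0.66 |
| 18 | 52% | 67% | 89% | 0.70 |
| 16 | 46% | 61% | 85% | 0.75 |

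The rows for 18 and 16 are illustrations (10% and 20% without a score); the plan gives no rate. The smallest n for 80% power is 34 at d = 0.5, 24 at 0.6 and 15 at 0.8. At d = 0.5 and n = 20 the gap to the stated figure is 80 - 56 = 24 points.

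**Step 2: looser forms of the same test at 0.5, n = 20.** The normal approximation gives 61% two-sided and 72% one-sided; the one-sided t-test gives 70%. None reaches 80%, and section 21 specifies two-sided tests.

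**Step 3: effect in baseline SDs.** With equal SDs at the two visits and correlation r between them, SD of change = baseline SD x sqrt(2(1 - r)). A shift of 0.5 baseline SD is then d = 0.5 / sqrt(2(1 - r)).

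| r | d | Power, n = 20 |
|---|---|---|
| 0.3 | 0.42 | 43% |
| 0.5 | 0.50 | 56% |
| 0.6 | 0.56 | 66% |
| 0.7 | 0.65 | 78% |
| 0.8 | 0.79 | 92% |

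Power reaches 80% when d = 0.6604, that is 2(1 - r) = (0.5 / 0.6604)^2 = 0.573, so r = 0.713.

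**Step 4: what a non-significant result would say.** The 95% confidence interval for the mean change has half-width 2.093 / sqrt(20) = 0.468 observed SDs of the change. A non-significant result would exclude 0.5 SD of benefit only if the observed mean change were below 0.5 - 0.468 = 0.032 SD in the direction of benefit.

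**The case against.** The strongest reply is that no stated figure is contradicted. The plan never defines moderate, and 0.66 lies between 0.5 and 0.8, so the phrase is a loose but fair description of a trial that detects 0.66 SD. Scaling by the baseline SD is just as ordinary, and with a correlation above about 0.71 the claim is true even at 0.5. This stands. A reader might infer from the 56% that the 80% is an arithmetic error of 24 points. The documents do not support that: the shortfall depends on defining moderate as 0.5 and on scaling by the SD of the change, and neither choice is theirs.

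A second reply is that a one-sample t-test may not be the intended analysis. Section 21 mentions an additional GLMM, and visits fall at weeks 4, 8 and 12. A four-visit repeated-measures F test with f = 0.25 gives 57%, 73% and 93% power at correlations of 0.3, 0.5 and 0.7. This stands in part. Such a model could do better, but again only with a correlation that the plan leaves out, and the power sentence itself refers to baseline-to-week-12 change.

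A reader might also infer that the plan expects losses and needs all 20 children to finish. The text is weaker than that. Section 22 only lists "Adverse effects from growth hormone administration, subject compliance, drop outs" as items to monitor. Section 9 keeps withdrawn children in every analysis and asks them to attend a final visit, so a withdrawal need not be a missing score. The section 7 label can mean the number needed for the study as a whole.

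Finally, this is a pilot, the sentence on adequate data is worded as a judgement and not derived from the power figure, and no section says how a non-significant result would be read. That limits the consequence, but it does not make the power sentence checkable.

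**Conclusion.** The point holds in a conditional form. The interaction named in the power statement cannot be tested in a single group. For the mean baseline-to-week-12 change with 20 children and two-sided .05, 80% power begins at 0.66 SD of the change. Power at 0.5 SD of the change is about 56%; at 0.5 of the baseline SD it lies between 43% and 92% for correlations from 0.3 to 0.8. The 80% claim is sound for the upper part of the moderate-to-large range. At the moderate end it needs a correlation a little above 0.71, which the plan neither states nor supports.

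This rests on the conventional meaning of moderate, on a one-sample t-test and, for the baseline-SD reading, on equal SDs at the two visits. It does not show that the investigators miscalculated, only that the statement is unqualified and cannot be verified.

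**What to change.** In section 7 (Feasibility of Meeting Recruitment Goals) and section 21 (Power Analysis), remove the treatment x time wording and the unqualified 80% claim, and put in their place:

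> With 20 children with week-12 scores, a two-sided .05 test of mean change in ABC-Social Withdrawal has 80% power for a mean change of 0.66 SD of the change scores (0.70 with 18, 0.75 with 16; these losses are illustrative assumptions). Power at 0.5 SD of the change is about 56%.

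Add that the mean change will be reported with its 95% confidence interval and that a non-significant result does not rule out a moderate effect. If the investigators had a baseline-SD effect or a longitudinal model in mind, they should state the correlation and its source and give the power on that basis.

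The replacement text treats ABC-Social Withdrawal as the single primary scale, as the Objectives do. The first endpoint in section 3 also lists the Repetitive Behavior Scale-Revised; if both were tested at .025 each (an assumption), the 80% threshold would be 0.74 SD.

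The cost is a wording change in two places. Enrolment stays at 20 and no procedure is added; the stated power simply looks less favourable.
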